5.4 RIS subject numbering

Each RIS subject will be uniquely identified by a combination of the originating center and study subject number. Upon signing the informed consent, the subject will be given a unique participant number by the participating center PI. For example, the first RIS participant at UT Southwestern Medical Center (Dallas, Texas, U.S.A.) would be assigned the following identification number: UTSW-001.

5.5 Database fields

The following data will be captured in this study via electronic data capture (EDC).

Clinical Data: Comprehensive demographic data (i.e. date of birth, sex, race and ethnicity, etc.) and clinical data (i.e. date of first clinical visit, reason for the initial MRI scan, findings from the patient's clinical examination (*to include vital signs*), Visual Systems Tests (low vision contrast charts, ocular coherence tomography (OCT)) CMP and CBC results, cerebrospinal fluid test results, new onset clinical attacks, extent of recovery, etc. will be obtained from face-to-face clinical visits and existing medical records. Cognitive/Functional assessments (*EDSS, expanded MSFC (Timed 25-FT Walk (T25-FW), 9-Hole Peg Test (9-HPT), Paced Auditory Serial Addition Test (PASAT-3 (3-second interval pause)), Symbol Digit Modalities Test (SDMT)*), will also be performed. Please refer to Appendix 1 – Cognitive/Functional Assessments

Patient Reported Surveys: Surveys containing questions related to Demographics, Family History, Lifestyle, Environment, and Environmental Exposure and the Neuro Quality of Life Questionnaire (*Neuro-QOL data*), will be completed by each study participant ; included will be inquiries into previous illnesses, the use of over-the-counter supplements, diet, occupational histories, exposure to vaccinations, etc. Please refer to Appendix 2 – Patient Reported Surveys.

Adverse events as well as concomitant medications will be collected and reported. All data collected for clinical assessments will be submitted via EDC and shared with Biogen. At the time of any patient withdrawing from the trial, an attempt will be made to determine the reason for discontinuation.

Radiological Data: Comprehensive radiological data will be collected from RIS subjects. Data to be incorporated into the study database include the date of the first MRI scan demonstrating anomalies within the brain that are suggestive of MS, number of lesions, lesion location, the presence of contrast enhancing lesions, the number of contrast enhancing lesions, changes observed between MRI studies, etc. In addition, data from the clinical MRI study of the cervical spine obtained at screening or Month 0 and at EOS will be incorporated if completed.

5.6 Detailed Patient Schedule of Assessments

Screening:

- Review of inclusion and exclusion criteria
- Evaluation of clinical and radiological data by the Core Clinical and Central Imaging Units
- Consent and Discussion of Study Expectations following approval for participation by the Centralized Units.

Week 0, +/- 2 weeks (approximately 2.5 hours)

- Record Demographics, and Medical and Clinical History
- Physical examination (including vital signs)
- Visual System tests (Low Vision Contrast charts, Ocular Coherence Tomography (OCT) (to be performed at UT Southwestern ONLY)
- Pregnancy test (urine)

- Cognitive/Functional Assessments (Appendix 1)
- Patient Reported Surveys (Appendix 2)
- Blood draw: CBC, CMP
- Biological mechanistic samples for future use (including DNA/RNA),
 - Serum
 - Spinal fluid (CSF) (optional)
- Standardized brain MRI at 1.5 or 3.0 Tesla
- Recommendation for MRI of the cervical spine with and without contrast (per medical standard of care)
- Obtain randomization number (1:1 Randomization of Tecfidera and Placebo)
- Administer Study Medication (including titration dosing)
- Review any adverse events and concomitant medications

Week 4, +/- 2 weeks (approximately 20 minutes)

- Telephone conversation
- Assessment for medical or medication difficulties
- Assessment of medication compliance
- Assessment of adverse events and changes in medications

Week 8, +/- 2 weeks (approximately 20 minutes)

- Telephone conversation
- Assessment for medical or medication difficulties
- Assessment of medication compliance
- Assessment of adverse events and changes in medications

Week 12, +/- 2 weeks: (approximately 20 minutes)

- Blood draw: CBC, CMP
- Assessment for medical or medication difficulties
- Assessment of medication compliance
- Assessment of adverse events and changes in medications
- Dispense Study Medication

Week 24, +/- 2 weeks: (approximately 20 minutes)

- Blood draw: CBC, CMP
- Assessment for medical or medication difficulties
- Assessment of medication compliance
- Assessment of adverse events and changes in medications
- Dispense Study Medication

Week 36, +/- 2 weeks: (approximately 20 minutes)

- Telephone conversation
- Assessment for medical or medication difficulties
- Assessment of medication compliance
- Assessment of adverse events and changes in medications
- Dispense Study Medication (via mail or patient pick up)

Week 48, +/- 2 weeks (approximately 1 hour):

- Review of Interval Medical History
- Physician examination (including vital signs)
- Visual System tests (Low Vision Contrast charts, Ocular Coherence Tomography (OCT) (to be performed at UT Southwestern ONLY)

- Cognitive/Functional Assessments (Appendix 1)
- Patient Reported Surveys (Appendix 2)
- Blood draw: CBC, CMP
- Biological mechanistic samples for future use (including DNA/RNA),
 - Serum
 - Spinal fluid (CSF) (optional)
- Standardized brain MRI at 1.5 or 3.0 Tesla (to be performed at UT Southwestern ONLY)
- Dispense Study Medication
- Review any adverse events and concomitant medications

Week 60, +/- 2 weeks: (approximately 20 minutes)

- Telephone conversation
- Assessment for medical or medication difficulties
- Assessment of medication compliance
- Assessment of adverse events and changes in medications
- Dispense Study Medication (via mail or patient pick up)

Week 72, +/- 2 weeks, (approximately 20 minutes):

- Blood draw: CBC, CMP
- Assessment for medical or medication difficulties
- Assessment of medication compliance
- Dispense Study Medication
- Review any adverse events and changes in medications

Week 84, +/- 2 weeks: (approximately 20 minutes)

- Telephone conversation
- Assessment for medical or medication difficulties
- Assessment of medication compliance
- Dispense Study Medication (via mail or patient pick up)
- Review any adverse events and changes in medications

Week 96, +/- 2 weeks (approximately 2 hours):

- Review of Interval Medical History
- Physician examination (including vital signs)
- Visual System tests (Low Vision Contrast charts, Ocular Coherence Tomography (OCT) (to be performed at UT Southwestern ONLY)
- Cognitive/Functional Assessments (Appendix 1)
- Patient Reported Surveys (Appendix 2)
- Blood draw: CBC, CMP
- Biological mechanistic samples for future use (including DNA/RNA),
 - Serum
 - Spinal fluid (CSF) (optional)
- Standardized brain MRI at 1.5 or 3.0 Tesla
- Recommendation for MRI of the cervical spine with and without contrast (per medical standard of care)
- Dispense Study Medication
- Review any adverse events and concomitant medications

Week 108, +/- 2 weeks: (approximately 20 minutes)

- Telephone conversation

- Assessment for medical or medication difficulties
- Assessment of medication compliance
- Review any adverse events and changes in medications
- Dispense Study Medication (via mail or patient pick up)

Week 120, +/- 2 weeks, (approximately 20 minutes):

- Blood draw: CBC, CMP
- Assessment for medical or medication difficulties
- Assessment of medication compliance
- Dispense Study Medication
- Review any adverse events and changes in medications

Week 132, +/- 2 weeks: (approximately 20 minutes)

- Telephone conversation
- Assessment for medical or medication difficulties
- Assessment of medication compliance
- Review any adverse events and changes in medications
- Dispense Study Medication (via mail or patient pick up)

Week 144, +/- 2 weeks (approximately 2 hours):

- Review of Interval Medical History
- Review of AEs and Concomitant Medications
- Physician examination (including vital signs)
- Visual System tests (Low Vision Contrast charts, Ocular Coherence Tomography (OCT) (to be performed at UT Southwestern ONLY)
- Cognitive/Functional Assessments (Appendix 1)
- Patient Reported Surveys (Appendix 2)
- Blood draw: CBC, CMP
- Biological mechanistic samples for future use (including DNA/RNA),
 - Serum
 - Spinal fluid (CSF) (optional)
- Standardized brain MRI at 1.5 or 3.0 Tesla
- Recommendation for MRI of the cervical spine with and without contrast (per medical standard of care)
- Collect all remaining study medication

Relapse Visit (approximately 2 hours):

- Review of Interval Medical History
- Review any adverse events and changes in medications
- Physician examination (including vital signs)
- Cognitive/Functional Assessments (Appendix 1)
- Patient Reported Surveys (Appendix 2)
- Blood draw: CBC, CMP
- Biological mechanistic samples for future use (including DNA/RNA),
 - Serum
- Recommendation for Standardized brain MRI at 1.5 or 3.0 Tesla at the discretion of the treating neurologist (per medical standard of care)

Unscheduled Visit (approximately 2 hours):

- Review of Interval Medical History
- Review any adverse events and changes in medications

- Physician examination (including vital signs)
- Cognitive/Functional Assessments (Appendix 1)
- Patient Reported Surveys (Appendix 2)
- If standard of care brain CBC, CMP obtained at this visit, data should be recorded.
- If standard of care brain and/or cervical spine MRI completed at this visit, data should be recorded.

Early Withdrawal/Discontinuation or End of Study (approximately 2 hours):

- Review of Interval Medical History
- Review any adverse events and changes in medications
- Physician examination (including vital signs)
- Visual System tests (Low Vision Contrast charts, Ocular Coherence Tomography (OCT) (to be performed at UT Southwestern ONLY)
- Cognitive/Functional Assessments (Appendix 1)
- Patient Reported Surveys (Appendix 2)
- Blood draw: CBC, CMP
- Biological mechanistic samples for future use (including DNA/RNA),
 - Serum
 - Spinal fluid (CSF) (optional)
- Standardized brain MRI at 1.5 or 3.0 Tesla
- Recommendation for MRI of the cervical spine with and without contrast (per medical standard of care)
- Collect all remaining study medication

Table. Summary of study related events by visit.

| Assessment | Screening | Week 0 | Week 4 | Week 8 | Week 12 | Week 24 | Week 36 | Week 48 | Week 60 | Week 72 | Week 84 | Week 96 |
|---|-----------|-----------|--------|--------|---------|---------|---------|-----------|---------|---------|---------|-----------|
| Informed Consent | X | | | | | | | | | | | |
| Review of Eligibility | X | | | | | | | | | | | |
| Evaluation by Clinical Core and Central Imaging | X | | | | | | | | | | | |
| Randomization | | X | | | | | | | | | | |
| Record History and Demographics | | X | | | | | | X | | | | X |
| Visual Systems tests | | UTSW only | | | | | | UTSW only | | | | UTSW only |
| Patient Reported Surveys | | X | | | | | | X | | | | X |
| Physical Exam (including vital signs) | | X | | | | | | X | | | | X |
| Cognitive/Functional Assessments | | X | | | | | | X | | | | X |
| Pregnancy Test (urine) | | X | | | | | | | | | | |
| Blood draw : CBC/CMP for safety screening (local lab for PI review) | | X | | | X | X | | X | | X | | X |
| Biological sample for DNA/RNA: SERUM | | X | | | | | | X | | | | X |
| CSF Samples (optional) | | X | | | | | | X | | | | X |
| Medication Assessment & Dispense rx via pt pick up or mail | | X | | | X | X | X | X | X | X | X | X |
| Brain MRI | | X | | | | | | UTSW only | | | | X |
| Cervical Spine MRI (optional – standard of care) | | SOC | | | | | | | | | | SOC |
| Telephone conversation | | | X | X | | | X | | X | | X | |
| Patient Compensation | | X | | | | | | X | | | | X |
| Review adverse events & changes in medication | | X | X | X | X | X | X | X | X | X | X | X |
| Collect remaining study medication | | | | | | | | | | | | |

- SOC: If standard of care MRI completed at this visit, data should be recorded
- CBC & CMP (safety labs): To be processed on-site for PI review and NOT shipped to UTSW
- Medication Assessment & Administration INCLUDES completion of 'Drug Accountability Record'
- If subjects who were consented for 96 weeks choose not to extend their participation through week 114/or EOS, their week 96 should be recorded as 'early withdrawal' visit.

| Assessment | Week 108 | Week 120 | Week 132 | Week 144 | Relapse | Early Withdrawal | Unscheduled |
|---|----------|----------|----------|-----------|---------|------------------|-------------|
| Informed Consent | | | | | | | |
| Review of Eligibility | | | | | | | |
| Evaluation by Clinical Core and Central Imaging | | | | | | | |
| Randomization | | | | | | | |
| Record History and Demographics | | | | X | X | X | X |
| Visual Systems tests | | | | UTSW only | | UTSW only | |
| Patient Reported Surveys | | | | X | X | X | X |
| Physical Exam (including vital signs) | | | | X | X | X | X |
| Cognitive/Functional Assessments | | | | X | X | X | X |
| Pregnancy Test (urine) | | | | | | | |
| Blood draw : CBC/CMP for safety screening (local lab for PI review) | | X | | X | X | X | SOC |
| Biological sample for DNA/RNA: SERUM | | | | X | X | X | |
| CSF Samples (optional) | | | | X | | X | |
| Medication Assessment & Dispense rx via pt pick up or mail | X | X | X | X | | | |
| Brain MRI | | | | X | SOC | X | SOC |
| Cervical Spine MRI (optional – standard of care) | | | | SOC | | SOC | SOC |
| Telephone conversation | X | | X | | | | |
| Patient Compensation | | | | X | | | |
| Review adverse events & changes in medication | | | | | X | X | X |
| Collect remaining study medication | | | | X | | X | |

5.7 Clinical exacerbations and radiological progression

All participating subjects will be advised to contact the lead site investigators if a clinical symptom is suspected or experienced in a RIS subject. Site PIs will be responsible for confirming clinical events and will perform the EDSS examination. Data will be entered via electronic data capture (EDC) for review by the Central Clinical Unit where the clinical exacerbation will be adjudicated. In the event of a suspected seminal acute or progressive demyelinating event, attempts will be made to evaluate the subject on an urgent basis within 48-72 hours from symptom onset by the site investigators (medical standard of care). Repeat imaging of the brain and spinal cord will be ordered at the discretion of the treating physician based on symptom localization and will be performed as per medical standard of care. Acute interventions (i.e. high-dose glucocorticosteroid treatment, etc.) will be prescribed and managed at the discretion of the treating physician at participating sites. The study visit will be labeled as either an “unscheduled visit” or a “relapse visit”. Study participant may be asked to provide additional biological specimens (serum) for future investigations. Sites will be encouraged to re-evaluate the patient within 3 months (medical standard of care) following the clinical event to assess the extent of recovery. All subjects who experience a seminal neurological event related to CNS demyelination, or those who are found to be intolerant to the study medication, will be provided with options highlighted in section 5.8.

RIS subjects will be made aware of any radiological progression identified on longitudinal imaging of the brain and spinal cord. As there is no FDA approved acute or long-term treatment for RIS, subjects will be extensively counseled by the PI as to their medical options.

5.8 Treatment options and safety monitoring following a confirmed relapse, intolerance to the study medication, or low absolute lymphocyte counts

5.8.1 When eligible, subjects on blinded study treatment who experience a confirmed clinical relapse by the Core Clinical Unit during the study will be offered the following options:

1. Remain on study treatment, with assignment remaining blinded
2. Prematurely discontinue blinded study treatment, begin treatment with Tecfidera (covered by Biogen up to 3-years from study enrollment date or until EOS) or subcutaneous peginterferon beta 1-a (Plegridy) if the study subject was randomized to Tecfidera, and remain in the study to complete a modified schedule of follow-up

Modified Schedule of Follow-Up:

- Re-evaluate patient within 3 mos of clinical event / relapse.
- Patient then presents every 12 weeks for post-relapse (PR) follow up; Week 48 PR, Week 96 PR etc, until original EOS date.

3. Prematurely discontinue blinded study treatment, decline open-label treatment with Tecfidera or Plegridy, and remain in the study to complete the schedule of follow-up evaluations. Original treatment assignment remained blinded

5.8.2 Dose reduction treatment option for intolerable flushing and/or gastrointestinal disturbances related to study medication:

Patient-reported complaints of persistent, intolerable flushing and/or gastrointestinal disturbance to blinded study medication will be asked to reduce the blinded study medication administration to one capsule twice daily for one month. Following the one-month reduction in

dose, patients will be asked to resume taking two capsules twice daily. If the patient is still unable to tolerate the blinded study treatment, the patient will be required to discontinue study treatment.

Any patient continuing to experience intolerance to study medication following the one-month reduction in dose will be offered a switch to Plegridy as an alternative therapy. The patient will be unblinded to the study medication at this time. Plegridy will be administered per FDA-dosing and titration instructions for relapsing forms of multiple sclerosis.

Any patient continuing to experience intolerance to study medication following the one-month reduction in dose, refusing a switch in therapy to Plegridy, and prematurely discontinuing dosing with blinded study treatment due to intolerance will be asked to consider remaining in the study and encouraged to continue participation in the trial on a modified schedule of assessments. Patient treatment will remain blinded.

Modified Schedule of Follow-Up:

- Re-evaluate patient within 3 mos of clinical event / relapse.
- *Patient then presents every 12 weeks for post-relapse (PR) follow up; Week 48 PR, Week 96 PR etc, until original EOS date.*

5.8.3 Parameters for low lymphocyte counts:

In the event that the absolute lymphocyte count is observed to be <500 cells/L during any time within the study, a repeat blood draw will be performed 3 months later. If a sustained reduction of the absolute lymphocyte count is observed (<500 cells/L), the study subject will be unblinded to the study medication and removed from the randomized portion of the trial. Repeat assessments will be performed monthly until the absolute lymphocyte count is >500 cells/L. Once the absolute lymphocyte count is found to be >500 cells/L, study subjects randomized to Tecfidera will be given the opportunity to receive Plegridy (covered by Biogen until study conclusion).

The rationale for providing these options to subjects was 2-fold: to conduct this placebo-controlled study ethically and to make every effort to continue to follow the subjects (for efficacy and safety evaluations), even after they discontinued the study treatment.

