5.3 Study Design

This is a multi-center, randomized, double-blinded study in which approximately 90 RIS subjects (refer to section 12 for sample size justification) will be treated with either Tecfidera or placebo (1:1 randomization) for 3 years or until End of Study (EOS) which is March 31, 2021. The primary outcome measure is the time to the first acute or progressive neurological event resulting from CNS demyelination. The secondary outcome measures include the number of new or enlarging T2 lesions, and the change in the number of contrast enhancing lesions, and T2-lesion and brain volumes. Study participants, along with the treating and examining physicians, will be blinded to treatment assignment. Central Clinical and Imaging Units will screen all potential study subjects for inclusion/exclusion criteria. We expect to enroll all RIS subjects within the U.S.

Following informed consent and verification of entry criteria by the core units, study participants will be randomized 1:1 to either Tecfidera (120mg by mouth twice daily for 7 days with dose escalation to 240mg by mouth twice daily) or placebo. Clinical follow-up by the treating physician, as defined within this protocol, will occur at weeks **0, 48, 96, 144 and/or EOS** and during or immediately following clinical exacerbations. (please refer to Study Schematic). During clinical visits comprehensive medical history data, safety labs, and optional biological samples will be obtained by the treating physician.

Patients will be scheduled for safety screenings (CBC & CMP) at weeks **12, 24, 72, 120**; at which time they will be seen by research coordinator or research nurse.

In addition to the face-to-face visits described above, study participants will be contacted over the telephone at weeks **4, 8, 36, 60, 84, 108, and 132** to assess for medical or treatment difficulties in addition to study medication compliance.

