8.1 Adverse Event Reporting

An adverse event is any untoward medical occurrence in a patient or clinical investigation subject administered a pharmaceutical product that occurs after first dose of study treatment through week 144 or EOS visit or early withdrawal/discontinuation visit, whether or not considered related to study treatment. Signs and symptoms existing prior to first dose and documented on the baseline Medical History form or Physical Examination Form are not considered AEs. Only baseline signs and symptoms that worsen while the subject is on the study drug are considered adverse events.

At every visit, participant will be questioned regarding the occurrence and nature of any adverse experiences. If any signs, symptoms or the results of the laboratory tests indicate an adverse effect, the study physician should determine the severity (grade) of the AE and judge the relationship to the study treatment according to the current version of the U.S. Department of Health and Human Services *Common Terminology Criteria for Adverse Events (CTCAE)*. In addition, if an adverse event necessitates medical care, appropriate care will be provided. Adverse events should be documented on the Adverse Event Report form, regardless of relationship to the study drugs. Notably, AEs thought to be due to treatment with the study drug are still reported as AEs in this study. The following information will be collected for all Adverse

Events:

- Start and stop dates
- Severity (See the Severity Grading section below)
- CTCAE score
- Relationship to study drugs (See the Association with the Study Drug below)
- Action taken with study drugs
- Treatment for the AE and outcomes

Severity Grading

For evaluation and reporting purposes, events will be graded by a numerical score according to their impact on the subject's ability to perform daily activities as follows:

- 1 - Mild (causing no limitation of usual activities)
- 2 - Moderate (causing some limitation of usual activities)
- 3 - Severe (causing inability to carry out usual activities)

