9. DATA SAFETY MONITORING BOARD (DSMB)

As Tecfidera is an approved FDA treatment for relapsing forms of multiple sclerosis, we do not anticipate any impediments to patient enrollment or significant adverse or serious adverse events. As a result, no data safety advisory board is required during the study.

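### The lymphocyte threshold in Section 5.8.3 is printed in cells per litre, so no non-zero blood count can trigger the retest, unblinding and removal rule as written

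*Protocol*

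**What the plan says.** Protocol Section 5.8.3 sets out a sequence of actions that all depend on one number.

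- **Repeat draw.** The sequence opens with "In the event that the absolute lymphocyte count is observed to be <500 cells/L during any time within the study". A second draw then follows three months later.
- **Unblinding and removal.** "If a sustained reduction of the absolute lymphocyte count is observed (<500 cells/L), the study subject will be unblinded to the study medication". The same sentence takes the subject out of the randomized portion of the trial.
- **End of rechecks.** "Repeat assessments will be performed monthly until the absolute lymphocyte count is >500 cells/L".
- **Plegridy offer.** "Once the absolute lymphocyte count is found to be >500 cells/L, study subjects randomized to Tecfidera will be given the opportunity to receive Plegridy". This step depends on recovery after a sustained low count; the low count itself does not trigger it.

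No other section gives a lymphocyte threshold, another numeric blood-count limit or a different unit.

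The counts come from the safety bloods. The visit table in Section 5.6 lists CBC and CMP at weeks 0, 12, 24, 48, 72, 96, 120 and 144 and at relapse and early-withdrawal visits. Its footnote reads: "CBC & CMP (safety labs): To be processed on-site for PI review and NOT shipped to UTSW". Section 4.1 plans 15 to 20 clinical sites. On independent oversight, Section 9 says: "As a result, no data safety advisory board is required during the study".

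**The concern.** A threshold expressed per litre is far below anything a routine blood count reports, so the two below-500 conditions and the two above-500 conditions cannot separate low counts from normal ones. The unit is the same at every use, so a site that doubts it finds no correct version elsewhere in the protocol.

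This matters statistically because the rule does more than prompt monitoring. It requires unblinding and removal from the randomized portion in a double-blind trial of about 90 subjects whose primary outcome is a time to event. Such a rule needs to be one that every site can apply exactly as written. Counts are read locally and no data safety board sits above the sites, so the protocol's text is the only thing that makes the rule uniform.

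**Working it through.** The protocol gives no calculation to reproduce here. The check is a unit conversion.

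**Inputs**
- Threshold: 500 cells/L (Section 5.8.3, four uses: below 500 twice, above 500 twice).
- Conversion: 1 L = 10^3 mL = 10^6 µL.
- Assumption, not in the documents: the smallest non-zero lymphocyte count that a laboratory reports lies between 0.001 and 0.1 ×10^9/L.

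**Step 1. The threshold in reporting units**
- 500 / 10^6 = 0.0005 cells/µL.
- 500 / 10^9 = 5 × 10^-7, that is 0.0000005 ×10^9/L.

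**Step 2. What that means physically**
- 1,000 mL / 500 cells = 2 mL of blood per lymphocyte.
- A 3 mL tube at the threshold would hold 500 × 3 / 1,000 = 1.5 lymphocytes.

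**Step 3. Distance from the smallest reportable count**

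| Assumed smallest non-zero report (×10^9/L) | In cells/L | Divided by 500 |
|---|---|---|
| 0.001 | 1,000,000 | 2,000 |
| 0.01 | 10,000,000 | 20,000 |
| 0.1 | 100,000,000 | 200,000 |

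**Step 4. The printed rule applied to example results**

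| Reported count (×10^9/L) | Below 500 cells/L? | Above 500 cells/L? |
|---|---|---|
| 0 | yes | no |
| 0.1 | no | yes |
| 0.4 | no | yes |
| 0.5 | no | yes |
| 1.5 | no | yes |

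As one worked case, 0.4 ×10^9/L is 4 × 10^8 cells/L, and 4 × 10^8 / 500 = 800,000 times the printed threshold.

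**Step 5. Consequence for each action**
- The repeat draw is triggered only by a reported zero.
- Unblinding and removal need the low count to be sustained at the repeat draw, so in practice a zero both times.
- The conditions for ending rechecks and for the Plegridy offer are met by any non-zero result. They are not reached at all unless the earlier steps have been triggered.

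The conclusion does not depend on where in the assumed range the reporting limit lies. The narrowest gap is still 2,000-fold.

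**The case against.** **The prefix may have been lost in reading the PDF.** The point rests on a single character before the L. A systematic loss would produce the same error at all four places, so repetition does not rule it out. Other special characters survive in the text: the superscript in Section 6, the degree sign in Section 14 and the less-than-or-equal sign in Section 12.1.2. That is some reassurance, but no micro sign appears anywhere in the protocol to test the matter directly, and the prior mean in Section 12.1.5 is spelled out as mu. A loss looks unlikely but cannot be excluded. This objection stands, and it makes the point conditional on a look at the source file.

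**No physician would take the unit literally.** This is largely fair. Most investigators would probably notice that the figure is implausible. Applying another unit is still a departure from the written rule, though, and Section 1 asks all study members to follow the stipulated procedures for the sake of consistency.

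**Other safeguards exist.** This is correct. Section 5.6 sends each CBC to the site PI. Section 8.1 has the study physician grade laboratory results that point to an adverse effect. Section 8.5 allows withdrawal when participation is judged no longer safe. Section 5.8.2 has its own route to unblinding, for intolerance. A reader might infer that this one number decides who is retested, unblinded or withdrawn, or that subjects are left without safety cover. The protocol does not support either reading. What is lost is the only numeric blood-count rule.

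**Effect on the comparison.** A reader might also infer that unblinding and removal would differ between sites, or fall mainly on the active arm. The protocol gives no lymphocyte results by arm or by site, so neither can be shown from it. It limits the later Plegridy offer to subjects randomized to Tecfidera, but that says nothing about how often low counts occur.

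**Conclusion.** The point holds, provided that the source PDF shows no prefix before the L. As printed, 500 cells/L equals 0.0005 cells/µL. No non-zero blood count falls below it and every non-zero count lies above it, so the rule in Section 5.8.3 cannot operate. To say that it can never be triggered would go slightly too far, because a result reported as zero would meet the first condition.

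The error is at least 2,000-fold under the assumed reporting limits. That ratio measures the notation and not an effect on the trial. The number of subjects concerned, and any effect on the primary time-to-event comparison, cannot be worked out because the protocol gives no frequency of low counts.

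It deserves correction ahead of ordinary typographical slips because the wrong figure is a decision threshold that mandates unblinding and removal from the randomized portion.

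**What to change.** 1. Check the source PDF of Section 5.8.3 for a unit prefix lost in text extraction. If it is there, the point falls away.
2. If it is not, the sponsor should confirm the intended value and unit.
3. Correct all four uses in Section 5.8.3 together, in the unit that the local laboratories report, with the SI equivalent beside each.
4. Notify all sites of the correction.

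This review does not say what the threshold should be. The cost is a short protocol correction and a site memo; design, sample size and visit schedule do not change.
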